- The risk specific to patients with SAA receiving eltrombopag is the potential for cytogenetic abnormalities. Clonal evolution is almost always an early event occurring within 6 months after initiation of eltrombopag in refractory SAA participants ([Winkler et al 2019](#)). The role of eltrombopag in the development of cytogenetic abnormalities in treatment-naïve SAA patients remains unknown. In Study CETB115AUS01T, clonal cytogenetic evolution occurred in 15/154 (10%) participants. Of the 15 participants who experienced cytogenetic abnormalities, 4 participants had chromosomal aberrations of unclear significance. 7 of these 15 participants had loss of chromosome 7, either alone or in combination with complex cytogenetic abnormalities, and in 6 of them, it occurred within the first 6.1 months. In 3 of the 7 participants this was accompanied by morphologic evidence of dysplasia or full myeloid malignant transformation. In 3 of 15 participants deletion of chromosome 13 was reported, considered to be a good prognostic factor in patients with aplastic anemia. One participant had a follow-up bone marrow assessment at 5 years which was markedly changed compared to prior bone marrow assessment, with features of dysplasia with hypercellularity concerning for potential development of myelodysplastic syndrome (MDS). It is unclear if these evolutions occurred due to the underlying disease, the IST and/or eltrombopag. In Study CETB115E1202, one cytogenetic abnormality was detected and it was not associated with dysplasia and increase in bone marrow blasts; no progression to MDS was reported. For the proposed protocol, bone marrow examination including cytogenetics will be performed at Week 13, Week 26, Week 52 and yearly after, as

described in [Section 8.4.3](#) and [Table 8-1](#). Development of new cytogenetic abnormalities must be documented and will result in permanent discontinuation of study treatment as described in [Section 9.1.1](#).

- There may be unforeseen risks with the study treatment which could be serious. These include but may not be limited to drug to drug interactions and long-term safety. Close adherence to eligibility criteria, study procedures safety monitoring and dose adjustment will help to minimize unforeseen risks. Potential for drug-drug interaction and measures to minimize undesired drug-drug interactions are described in [Section 6.2.1](#) and [Section 6.2.2](#).

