8.1 Screening

All participants will be screened for study eligibility. All participants must sign an informed consent prior to any screening procedures being performed.

Activities for screening will begin up to 30 days prior to initiation of study treatment with eltrombopag, r-ATG and CsA. During this time, all participants will complete a bone marrow aspirate and biopsy to confirm current SAA diagnosis. The sample of bone marrow aspiration and biopsy, and the result of cytogenetic analysis obtained within 30 days prior to Day 1 can be used for evaluation, and the results will be used as baseline value. The criteria for diagnosis of SAA are found in [Section 5.1](#). Cytogenetic analysis and all other analyses will be completed to verify inclusion and exclusion criteria.

An evaluable karyotyping is mandatory for the eligibility assessment. Eligibility must be based on a normal karyotype of at least 10 metaphases. If 10 metaphases are not seen, the bone marrow aspirate must be repeated. The participant won't be eligible if the karyotyping fails again by the second bone marrow aspiration due to insufficient metaphases.

In addition to conventional karyotyping, FISH should be performed to detect abnormalities in chromosome 3, 5, 7, 8 and those associated with SAA, MDS, acute myeloid leukemia (AML) etc. Candidate participant may start with the investigational treatment if a normal karyotyping result is shown for eligibility assessment while waiting for the FISH result. In case the FISH result comes out to be abnormal indicating cytogenetic abnormalities, the participant must be discontinued from the study treatment.

Information regarding eligibility criteria will be collected on the Inclusion/Exclusion eCRF. Participants who do not meet all entry criteria should not be entered into the study.

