9.1 Discontinuation

9.1.1 Discontinuation of study treatment

Discontinuation of study treatment for a participant occurs when study treatment is permanently stopped earlier than the protocol planned duration and can be initiated by either the participant or the investigator.

The investigator must discontinue study treatment for a given participant if, he/she believes that continuation would negatively impact the participant's well-being.

Study treatment must be discontinued under the following circumstances:

- The hematologic response is assessed as NR at Week 26.
- Diagnosis of relapse.
- Participant/guardian decision.
- Pregnancy.
- Any of the following is observed: a new clinical significant morphological, chromosomal or cytogenetic abnormality*, diagnosis of myelofibrosis^{**} or progression to MDS or AML.
- Participant meets any of the stopping criteria in [Section 6.5.1](#).
- Any laboratory abnormalities that in the judgment of the investigator, taking into consideration the participant's overall status, prevents the participant from continuing the study treatment.
- Use of prohibited treatment as per recommendations in the prohibited treatment section (see [Section 6.2.2](#)).
- The participant is withdrawn from the treatment with planned r-ATG or CsA, or the participant cannot tolerate the planned study treatment (e.g. Infusion-related r-ATG reactions refractory to all appropriate supportive measures; Life threatening acute hypersensitivity reactions).
- The participant has an unacceptable AE whose causal relationship with eltrombopag cannot be ruled out.
- The participant is found to be significantly non-compliant with the requirements of the protocol (including treatment non-compliance).
- The investigator (or sub-investigator) believes that the participant will not benefit from eltrombopag or
- that the participant needs to transfer to other therapy (e.g. HSCT, ATG/ALG).
- The study is prematurely terminated.
- Any situation in which study participation might result in a safety risk to the participant.

*: Discontinuation should be considered if any new chromosomal or cytogenetic abnormality is observed, and if considered significant should be discontinued. This also applies for participants that started treatment based on normal karyotyping while FISH results were not yet available.

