**: Considering TPO-receptor agonists like eltrombopag might lead to pathological increase in reticulin or collagen fibers by chronic stimulation of megakaryocytes. It is highly recommended to consider discontinuation of eltrombopag if a pathological myelofibrosis (e.g. staining for fibrosis is Grade 3 or higher) is confirmed.

Participants may voluntarily discontinue from the study treatment (eltrombopag and/or r-ATG and/or CsA) for any reason at any time. If discontinuation of study treatment occurs, the investigator should make a reasonable effort to understand the primary reason for the participant's premature discontinuation of study treatment and record this information.

Participants who discontinue study treatment or who decide they do not wish to participate in the study further should NOT be considered withdrawn from the study UNLESS they withdraw their consent (see [Section 9.1.2](#)). **Where possible, they should return for the assessments indicated** in the Assessment Schedule. If they fail to return for these assessments for unknown reasons, every effort (e.g. telephone, e-mail, letter) should be made to contact the participant/pre-designated contact as specified in the lost to follow-up section (see [Section 9.1.3](#)). This contact should preferably be done according to the study visit schedule.

If the participant cannot or is unwilling to attend any visit(s), the site staff should maintain regular telephone contact with the participant, or with a person pre-designated by the participant. This telephone contact should preferably be done according to the study visit schedule.

After study treatment discontinuation, at a minimum, in abbreviated visits, the following data should be collected at clinic visits or via telephone/email contact:

- New / concomitant treatments
- AEs / SAEs
- Clonal evolution assessments

The investigator must also contact the IRT to register the participant's discontinuation from study treatment.

Participants who prematurely discontinue study treatments will have efficacy assessments at defined time points (Week 13, Week 26, Week 52 and yearly after), unless or until the occurrence of no response at Week 26, relapse or alternative SAA treatment (whichever comes first). Survival and clonal evolution data will be collected for all participants up to Year 3 (Week 156).

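### Protocol stopping rules for an abnormal FISH result after starting treatment, and for myelofibrosis, differ between passages in obligation, threshold and object

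*Protocol*

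**What the plan says.** **Abnormal FISH after starting.** Section 8.1 of the protocol lets a candidate start on a normal karyotype before FISH is back, and then says: "In case the FISH result comes out to be abnormal indicating cytogenetic abnormalities, the participant must be discontinued from the study treatment". Section 9.1.1 covers the same people in its cytogenetics footnote. That footnote reads "Discontinuation should be considered if any new chromosomal or cytogenetic abnormality is observed, and if considered significant should be discontinued" and continues "This also applies for participants that started treatment based on normal karyotyping while FISH results were not yet available". Exclusion criterion 3 in Section 5.2 bars any cytogenetic abnormality on karyotyping or FISH, without a significance test.

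**Myelofibrosis.** The list in Section 9.1.1 opens with "Study treatment must be discontinued under the following circumstances" and includes "a new clinical significant morphological, chromosomal or cytogenetic abnormality*, diagnosis of myelofibrosis". The footnote attached to myelofibrosis says: "It is highly recommended to consider discontinuation of eltrombopag if a pathological myelofibrosis (e.g. staining for fibrosis is Grade 3 or higher) is confirmed".

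**New on-study cytogenetic abnormality.** Section 4.5 says: "Development of new cytogenetic abnormalities must be documented and will result in permanent discontinuation of study treatment", and refers the reader to Section 9.1.1. The list there is limited to clinically significant abnormalities.

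Section 6.1 defines study treatment as eltrombopag, r-ATG and CsA together. Section 6.5.1 points to Section 9.1.1 for the events at which permanent discontinuation is mandatory.

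**The concern.** Section 4.5 names hematological malignancy, marrow reticulin formation and cytogenetic abnormality as risks specific to eltrombopag, and relies on stopping rules among its mitigations. For two of the triggers, an investigator gets a different instruction depending on which passage is open. A participant whose baseline FISH turns out abnormal meets an exclusion criterion. Section 8.1 takes that participant off treatment, while the footnote leaves room to continue.

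The object also matters. r-ATG is finished by Day 5, but Section 6.1.5 plans CsA to at least Year 2. Whether a rule stops study treatment or eltrombopag therefore decides whether CsA stops too.

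The choice of passage reaches the data in three ways:

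- The last eltrombopag dose fixes the end-of-treatment visit and the on-treatment period (Protocol Section 12.5.2; Section 2.1.1 of both SAPs).
- Laboratory summaries, as worded in SAP Section 2.8.3, run to 30 days after the last study treatment, so the object of the rule can move that window.
- Protocol deviations are tabulated (SAP Section 2.3.1). The same conduct would comply with one passage and deviate from another.

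**Working it through.** The plan gives no figure of its own on this point. The check sets the current passages side by side and then sizes the one trigger for which the protocol offers a rate.

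| Trigger | Passage | Obligation | Threshold | Object |
|---|---|---|---|---|
| Abnormal FISH after start | 8.1 | must | any abnormal result indicating cytogenetic abnormality | study treatment |
| Abnormal FISH after start | 9.1.1 cytogenetics footnote | consider; should if significant | significance judged | not restated |
| Myelofibrosis | 9.1.1 list | must | diagnosis, no grade | study treatment |
| Myelofibrosis | 9.1.1 myelofibrosis footnote | highly recommended to consider | confirmed pathological, e.g. Grade 3 or higher | eltrombopag |
| New on-study abnormality | 4.5 | will result in | any new abnormality | study treatment |
| New on-study abnormality | 9.1.1 list | must | clinically significant | study treatment |
| New on-study abnormality | 9.1.1 cytogenetics footnote | consider; should if significant | significance judged | not restated |

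**FISH.** Both passages are operative and address the same participants. Section 8.1 does not refer to Section 9.1.1. They agree on the direction when the abnormality is judged significant (must against should) and part when it is not.

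**Myelofibrosis.** Both texts sit in Section 9.1.1, and obligation, threshold and object all differ. The cross-reference in Section 6.5.1 does not settle it, because it leads back to the same divided section. Marrow is sampled at Weeks 13, 26 and 52 and yearly. Eltrombopag is provided only to Week 52, so for a finding after that point the footnote leaves nothing to stop, while the list could still stop CsA.

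**New on-study abnormality.** For a significant abnormality, all three texts point towards stopping. They diverge mainly when the abnormality is not judged significant. Inputs from Section 4.5 for the pivotal study are 15 of 154 participants with clonal cytogenetic evolution, of whom 4 had aberrations of unclear significance and 3 had a chromosome 13 deletion described as a good prognostic factor. With 36 participants here:

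- Unclear significance only: 36 × 4/154 = 0.9.
- Adding the chromosome 13 deletions: 36 × (4 + 3)/154 = 36 × 7/154 = 1.6.
- All clonal events, for comparison: 36 × 15/154 = 3.5.

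The second line assumes the two groups do not overlap. Section 4.5 does not say so. Its four descriptions do add to the total (4 unclear, 7 with loss of chromosome 7, 3 with chromosome 13 deletion, and 1 with late marrow change: 4 + 7 + 3 + 1 = 15), which is consistent with no overlap but does not prove it.

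**The case against.** **The cytogenetics footnote is stronger than it first looks.** A reader might infer that it makes stopping optional throughout. It does not: a significant abnormality should lead to discontinuation, so for significant findings the gap within Section 9.1.1 is only between must and should. This stands and confines the cytogenetic conflict mainly to abnormalities not judged significant.

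**Section 4.5 is a risk summary that defers to Section 9.1.1.** This also stands. The governing section for new on-study abnormalities can be identified, which makes that mismatch the lesser one.

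**Section 8.1 is the specific rule for FISH, and few people can be affected.** The rationale for Amendment 3 describes discontinuation in this situation as required. It also reports last patient first visit on 03-Dec-2021 and enrollment complete with 36 participants, before the amendment date of 22-Dec-2021. The size argument stands: few if any FISH results could still have been outstanding. The rationale, however, is not the operative text, and the footnote expressly names these participants in the section an investigator would consult about stopping.

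**Other parts of Section 9.1.1 act as backstops.** It separately requires stopping for progression to MDS or AML, for any situation that might create a safety risk, and where continuing would harm the participant's well-being. The conflict therefore does not leave participants unprotected.

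**Stronger readings the documents do not support.** A reader might take 15/154 and infer that 3 to 4 of the 36 are affected. That counts every clonal event, including those where all passages point to stopping. A reader might also infer that observed clonal evolution depends on the passage followed. For the on-study cytogenetic rule, the first clonal event is itself the trigger and precedes the decision. It must be recorded as an adverse event (Section 10.1.1), and cytogenetic assessment continues regardless of disposition (Section 8.4.4).

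**Conclusion.** The contradiction is real in the current protocol for two triggers: abnormal FISH after starting on a normal karyotype (Section 8.1 against the 9.1.1 cytogenetics footnote), and myelofibrosis (the 9.1.1 list against its footnote). The Section 4.5 wording on new on-study abnormalities is a lesser inconsistency.

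The numbers are small. For new on-study abnormalities, the passages lead to different actions for about 1 to 2 of 36 participants. This assumes that the pivotal-study mix carries over although that study used h-ATG, that unclear and possibly chromosome 13 findings would be judged not significant, and that they arise while treatment continues. The last assumption is generous, because Week 26 non-responders stop anyway. The documents give no rate of post-start abnormal FISH or of myelofibrosis, so those two cannot be sized.

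The consequences are inconsistent handling between sites, possible continued treatment of a participant who meets an exclusion criterion, and exposure, on-treatment windows and deviation counts that depend on the passage followed. The primary estimate is not directly changed: treated participants stay in the full analysis set (Section 12.1). Efficacy assessments also continue after discontinuation until no response at Week 26, relapse or alternative treatment (Section 9.1.1).

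Nothing here says which of the clinical rules is correct, only that the passages cannot all be followed.

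**What to change.** Reconcile Section 4.5, Section 8.1, the Section 9.1.1 list and both Section 9.1.1 footnotes. Each trigger (abnormal baseline FISH found after starting, new on-study cytogenetic abnormality, myelofibrosis) should have one rule, one threshold and one stated object, either study treatment or eltrombopag. The sponsor's clinical team must choose the rules.

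The change is a few sentences. Under Section 14.1 it still needs a written amendment with sponsor approval, health authority approval where required and IRB/IEC approval, followed by notification to sites. No sample size or planned analysis changes.

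Where conduct is already past the point at which wording could alter practice, the study report can list each participant who met one of these triggers, the action taken for each drug and its date, and state which passage was used to classify deviations. The SAPs already plan listings of marrow data and narratives for new cytogenetic abnormalities, so the added work is slight.

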9.1.1.1 Replacement policy

Participant will not be replaced on study.

9.1.2 Withdrawal of informed consent

Participants may voluntarily withdraw consent to participate in the study for any reason at any time. Withdrawal of consent occurs only when a participant:

- Does not want to participate in the study anymore,
and
- Does not want any further visits or assessments
and

- Does not want any further study related contacts

In this situation, the investigator should make a reasonable effort (e.g. telephone, e-mail, letter) to understand the primary reason for the participant's decision to withdraw his/her consent and record this information.

Study treatment must be discontinued and no further assessments conducted, and the data that would have been collected at subsequent visits will be considered missing.

Further attempts to contact the participant are not allowed unless safety findings require communicating or follow-up.

All efforts should be made to complete the assessments prior to study withdrawal. A final evaluation at the time of the participant's study withdrawal should be made as detailed in the assessment table.

Novartis will continue to keep and use collected study information (including any data resulting from the analysis of a participant's samples until the time of withdrawal) according to applicable law.

For Japan: All biological samples not yet analyzed at the time of withdrawal may still be used for further testing/analysis in accordance with the terms of this protocol and of the informed consent form.

For China, Korea and Taiwan: All biological samples not yet analyzed at the time of withdrawal will no longer be used, unless permitted by applicable law. They will be stored according to applicable legal requirements.

9.1.3 Lost to follow-up

For participants whose status is unclear because they fail to appear for study visits without stating an intention to discontinue or withdraw, the investigator must show "due diligence" by documenting in the source documents steps taken to contact the participant, e.g. dates of telephone calls, registered letters, etc. A participant should not be considered as lost to follow-up until due diligence has been completed or until the end of the study.

9.1.4 Early study termination by the sponsor

The study can be terminated by Novartis at any time. This may include reasons related to the benefit/risk assessment of participating in the study, practical reasons (including slow enrollment), or for regulatory or medical reasons.

Reasons for early termination:

- Unexpected, significant, or unacceptable safety risk to participants enrolled in the study;
- Decision based on recommendations from applicable board(s) after review of safety and efficacy data;
- Discontinuation of investigational drug development.

In taking the decision to terminate, Novartis will always consider the participant welfare and safety. Should early termination be necessary, participants must be seen as soon as possible and treated as a prematurely withdrawn participant. The investigator may be informed of additional procedures to be followed in order to ensure that adequate consideration is given to the

protection of the participant's interests. The investigator or sponsor depending on the local regulation will be responsible for informing IRBs/IECs of the early termination of the trial.

9.2 Study completion and post-study treatment

Study completion is defined as when the last participant finishes her/his Study Completion visit, and any repeat assessments associated with this visit have been documented and followed-up appropriately by the Investigator, or in the event of an early study termination decision, the date of that decision.

All treated participants should have a safety follow-up visit conducted 30 days after last administration of eltrombopag. The information collected is kept as source documentation. All SAEs reported during this time period must be reported as described in [Section 10.1.3](#). Documentation of attempts to contact the participant should be recorded in the source documentation.

The primary analysis will be performed after all participants have completed Week 26 or discontinued prior to Week 26. The primary analysis data will be summarized in the primary clinical study report (CSR). Following the cut-off date for the analysis reported in the primary CSR, the study will remain open. Ongoing participants will continue to receive study treatment and be followed as per the schedule of assessments, as long as participants derive benefit from eltrombopag.

The end of study defined as the earliest occurrence of one of the following:

1. All participants have died or discontinued from the study or complete the study participation per protocol.
2. Another clinical study becomes available that can continue to provide eltrombopag in this participant population and all participants ongoing are eligible to be transferred to that clinical study.

At the end of Year 2 in this study, participants who in the opinion of the Investigator are still deriving clinical benefit from further CsA treatment should be directed by the treating physician to receive the product through commercial channels locally. The final analysis will occur at the end of the study. All available data from all participants up to this cut-off date will be analyzed and summarized in a final CSR.

10 Safety monitoring and reporting

